Effectiveness and Cost-effectiveness of the Check Your Health Preventive Programme

NCT – 02028195

Approved 21-08-2018

NCT – 02028195

Statistical analysis plan for evaluation of Check your Health Preventive Programme, 2018
Approved 21-08-2018

Statistical Analysis Plan

Check Your Health Preventive Program

Evaluation of a preventive health promotion strategy performed in a primary care and municipality setting

2018

NCT-number: 02028195

Statistical analysis plan for evaluation of Check your Health Preventive Programme, 2018
Approved 21-08-2018

1. Introduction

The Check Your Health Preventive Program (CHPP) was set up to investigate the effectiveness on health outcomes of a preventive health check offered at a population-level to all individuals aged 30-49 years in a large municipality (approximately 26.000 citizens) (1).

Studies have indicated that preventive health checks are likely to reduce CVD risk (2) and to be cost effective (3,4). However, a recent Cochrane review found no reduction in mortality, CVD or cancer in follow-up of preventive health checks (5). Concerns have been raised that the review had significant methodological problems (e.g. weak package of screening tests, primary outcome not appropriate for the diverse set of screening tests) and was mainly based on 20 to 30 years old studies (6). Although, there was no consensus on the effect of preventive health checks e.g. the UK National Health Service Health Check program has been introduced to all citizens aged 40 to 74 years to assess individual disease risk in routine care (7,8).

The objective of the pragmatic household cluster-randomised controlled trial, Check Your Health Preventive Program, was to investigate the effectiveness on health outcomes of preventive health checks at a population level to all individuals aged 30 to 49 years in a primary care setting.

The trial is registered at ClinicalTrials.gov ID: NCT02028195 (7 March 2014).

This is the plan for statistical analysis of the impact of the population-based health check on health outcomes after a 4 years follow-up.

2. Aim

The aim is to evaluate:

Effectiveness of the population-based Check Your Health Preventive Programme conducted in primary care on CVD-risk, physical activity, self-rated health and functional capacity.

3. Outcome measures

Outcome measures are assessed based on information from self-reported questionnaire, from measurements at the health examination and from national registers.

3.1. CVD risk

CVD risk was assessed based on European Heart-SCORE ten-year-risk of fatal cardiovascular event (8). The score is derived from information on age, gender, smoking status, systolic blood pressure and total cholesterol for each individual. CVD risk will be analysed as a continuous measure.

3.2. Physical activity

- a) Self-reported physical activity was assessed by the use of questionnaire as days/week with a minimum of 30 minutes moderate physical activity. It takes values in the range 0-7 days and will be analysed as a continuous measure.
- b) Cardiorespiratory fitness (ml O₂/kg/min) was measured using Aastrand's submaximal bike-test and will be analysed as a continuous measure.

3.3. Self-rated health

Self-rated health was measured by the use of Short-form 12 (SF12) (10).

- a) Self-rated health is assessed from the first question in SF12 ("In general, would you say your health is: excellent, very good, good, fair or poor") and will be dichotomized (1 = excellent, very good and good, 0 = fair and poor) and analysed as a binary measure.
- b) Mental health was assessed by the Mental Component Score (MCS) from SF12 and analysed as a continuous measure.

3.4. Functional capacity

Functional Capacity (sick leave, working status), affiliation to the labour market (work participation in the last year) will be assessed based on the national register of social transfer payments (DREAM).

Work participation will be described as a fraction of full-time employment in the 52 weeks before the invitation date and analysed as a continuous measure.

Sick leave will be measured as a dichotomous variable and as categories of number of sick-leave periods over 3 weeks during the last year before invitation date.

4. Analysis Population

[figure not shown]

Figure 1. Participants in Check your Health Preventive Programme, Randers

NCT-number: 02028195

Statistical analysis plan for evaluation of Check your Health Preventive Programme, 2018

Approved 21-08-2018

All citizens aged 30-49 years in the municipality of Randers on January 1, 2012 were randomized into five groups (n=26,216) (Figure 1).

The trial was performed as a pragmatic household-cluster randomized controlled trial and included 10,505 individuals. The Intervention group (IG) was defined as the population invited to attend the health check in year 2 and re-invited in year 5, whereas the comparison group (CG) was defined as the population invited to attend in year 5.

A total of 55% of the invited population participated in the health check in year 1, 2012-2013 (11). We expect a similar proportion of the population will participate in the following years.

The actual study population will differ according to the different outcome measures:

CVD risk and cardiorespiratory fitness: The study population is all individuals from the IG, who participated in both baseline and re-examination, and all individuals from the CG, who participated in the examination.

Self-reported health and self-reported physical activity: The study population is all individuals from the IG, who completed both the baseline and the re-examination questionnaire, and all individuals from the CG, who completed the questionnaire.

Functional capacity: The study population is all individuals from IG, who participated in both baseline and re-examination, and all individuals from the CG, who participated in the examination.

5. Descriptive Analysis

To investigate participation patterns in the initial health check we analyze the binary participation status for the first invitation with respect to characteristics of the invited cohort (age, sex, socio-economic status, etc) in a logistic regression.

Intervention and comparison group will be characterized with respect to baseline demographics. For continuous variables, we report their means and standard deviations (SD), when their distribution is approximately normal, whereas for variables with skewed distributions we report medians and interquartile range (IQR). For categorical variables, we report frequencies and their percentage of the total.

6. Analysis of study outcome measures

For the outcomes, which are only measured for participants in the re-examination (CVD risk, physical activity and self-rated health), we will in addition use a multiple imputation and propensity score based analytic strategy as follows. In the first step, we will use multiple imputation to impute missing values for all who participated in the health checks when randomized to receive it (IG or RG).

Missing data

Frequency and patterns of missing outcome data will be reported with information on reasons (did not receive health check, did not answer question). Missing data are not assumed to be 'missing completely at random', so excluding individuals with missing information will likely introduce selection bias. Multiple imputation will be performed for missing outcomes as described in section 4 by inclusion of baseline characteristics that can explain the missingness. Subsequently, we will treat the missingness mechanism as

at random given the observed information (the Missing At Random (MAR) assumption) and use MICE (12) for multiple imputation and perform analyses after Rubin's rules (13). We will explore the robustness of estimates towards violations of the MAR by conducting sensitivity analyses by, for example, assuming that individuals with an unreported level of physical activity on average have one day less of 30 minutes activity than would have been predicted from their observed covariates. The mimicked analysis based on outcomes available from register-data also allows assessment of the potential violation of the MAR assumption.

Propensity score

Among all individuals in IG who participated in year 2 examination, we predict the likelihood of participation in the re-examination in year 5. For the participants of the IG in their first health check, we will estimate how their participation in the re-examination depends on their individual characteristics and measurements obtained in the first health check (sex, age, CVD risk, physical activity, etc). This logistic regression will rely on the multiply imputed datasets. Based on the obtained estimates, the propensity for participating in a re-examination is predicted for all in the IG and the CG who participated in the initial health check they were invited to. We will examine the balancing properties of the propensity score obtained, before we use it to weigh the analysis of treatment effect for the various outcomes (CVD risk, physical activity and self-rated health). The model will be developed based on IG and used in CG to perform effect estimation among comparable groups. All analyses will estimate average treatment effects expressed as mean differences for continuous outcomes and absolute risk differences for binary outcomes. We will finally assess the capacity of the propensity score to remove bias in estimated treatment effects by mimicking this analytic strategy for the functional capacity outcomes, and comparing with the estimates obtained for these outcomes when considering the entire invited population.

The treatment effects associated with participation in CHPP will be reported for each outcome measure with 95% confidence intervals. All analyses will account for clustering at household level.

7. Timescale

Analyses plan will be uploaded to clinicaltrials.gov before 15th September 2018.

Preliminary analyses will be performed before 1st April 2019 and final analysis during 2019.

8. Perspectives

The following analyses are planned and will be described separately:

- a) Comparison of health outcomes in CHPP with other municipalities matched on sex, age and educational level.
- b) Cost-effectiveness analysis (direct and total costs, live-years saved, expected life-years gained, GP utilization/hospital admissions)
- c) CHPP effect on CVD and mortality

9. References

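### For the measured and questionnaire outcomes, section 4 requires two attendances in the intervention group but one in the comparison group, and section 6 does not assuredly repair the imbalance

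*SAP*

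**What the plan says.** Section 4 defines the arms by invitation. "The Intervention group (IG) was defined as the population invited to attend the health check in year 2 and re-invited in year 5"; CG is invited in year 5 only. The whole IG, including those who did not come in year 2, therefore gets a year-5 invitation.

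The analysis sets are then defined by attendance. For the examined outcomes: "CVD risk and cardiorespiratory fitness: The study population is all individuals from the IG, who participated in both baseline and re-examination", together with every CG member who was examined. For self-rated health and self-reported activity, the set is IG members "who completed both the baseline and the re-examination questionnaire, and all individuals from the CG, who completed the questionnaire".

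For CVD risk, physical activity and self-rated health, section 6 states that "we will in addition use a multiple imputation and propensity score based analytic strategy". The steps are:

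- **Imputation:** "we will use multiple imputation to impute missing values for all who participated in the health checks when randomized to receive it".
- **Score:** a logistic model for return in year 5, fitted in IG year-2 attenders on personal characteristics and "measurements obtained in the first health check (sex, age, CVD risk, physical activity, etc".
- **Application:** the score is "predicted for all in the IG and the CG who participated in the initial health check they were invited to". Its balancing properties are examined "before we use it to weigh the analysis of treatment effect for the various outcomes".
- **Benchmark:** the same strategy is tried on the register outcomes and compared with the estimate for everyone invited.

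Section 6 reports effects of participation. The Introduction states a population-level objective.

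**The concern.** Two different filters are applied to two randomised groups. An IG member who missed year 2 and came in year 5 has a measured outcome and is discarded. The CG member who would have behaved the same way is kept. If repeat attenders differ in health from one-time attenders, the arms differ with no effect of the programme at all.

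Section 6 is the plan's answer, but it leaves three gaps. The year-2 skippers are outside the scored group. A CG member's first check is the year-5 check, so the CVD risk and activity values entering the CG score are the outcomes being compared. And the SAP does not say whether the weight is p or 1/p, which arm is weighted, or whether the section 4 or the section 6 analysis is the main one. At stake are the interpretation of these outcomes as a randomised comparison and the lack of any direct analysis of the population-level objective for them.

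**Working it through.** **Who is dropped.** Inputs from section 4: 26,216 randomised to five groups, 10,505 in the trial, 55% attendance in year 1 and a similar share expected later. Two of five groups gives 26,216 x 2/5 = 10,486, against 10,505 stated (0.2% apart), so the figures agree. Assumptions: an equal split, 55% attendance in both arms in each round, and a share r of IG year-2 attenders returning (r is not given).

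- Per arm: 10,505 / 2 = 5,252.5. Attenders per round: 0.55 x 5,252.5 = 2,889.
- The IG set is 2,889r. IG people with year-5 outcomes who are dropped number 2,889(1 - r). CG keeps all 2,889.

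| r | IG kept | IG dropped with a year-5 outcome | SE of difference (SD units) |
|---|---|---|---|
| 0.55 | 1,589 | 1,300 | 0.031 |
| 0.70 | 2,022 | 867 | 0.029 |
| 0.90 | 2,600 | 289 | 0.027 |

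The SE is sqrt(1/n_IG + 1/n_CG) and ignores household clustering.

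**Does section 6 remove the imbalance?** This was checked with null models, with no programme effect. Health is standard normal at years 2 and 5. First attendance is logistic in current health plus a personal habit of attending and is set to 55%; the odds ratio is 0.6 to 0.8 per SD worse health. The score is a logistic model of return on year-2 health in IG, applied to year-5 values in CG. CG is weighted by p, the form that fitting in IG and applying in CG suggests. Return among IG year-2 attenders follows (A) current health, (B) year-2 results, or (C) habit only. Entries are differences in SD, plus favouring IG. The second, third and fifth columns use correlations 0.5 and 0.8, with return of 55% to 91%.

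| Return follows | Section 4 sets, unweighted | CG weighted by p | CG by p, correlation 0.95 | All year-5 attenders, both arms |
|---|---|---|---|---|
| A | -0.03 to +0.16 | about 0 | about 0 | about 0 |
| B | -0.09 to +0.11 | -0.21 to -0.02 | -0.02 to 0.00 | -0.07 to -0.01 |
| C | -0.15 to -0.02 | -0.11 to -0.01 | -0.01 to 0.00 | -0.12 to -0.05 |

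With weights from a register covariate correlated 0.3 to 0.6 with health, the last column hardly changes (the near end in C becomes -0.04). Adding imputation of the non-returners' year-5 values, with p-weights in both arms, leaves the CG-by-p ranges unchanged to within 0.001.

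The pattern has a simple reason. In A the two IG attendances follow the same rule, so they are interchangeable, and weighting CG's one attendance by p reproduces selection on both. In B the score acts at full strength on CG's year-5 value. In IG, selection on year-2 health reaches year-5 health only through the correlation. CG is then pushed too far towards the healthy, and IG looks worse. As the correlation approaches 1 this gap closes.

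A mixed model had return depending equally on year-2 and year-5 health (log-odds 0.2 to 0.6 per SD, correlation 0.5 or 0.7, return 0.60 or 0.75). It gave -0.12 to -0.03 with CG weighted by p and -0.07 to -0.01 with IG returners weighted by 1/p. Neither form reliably returned zero.

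**The case against.** Much of the case for the plan stands.

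- **A participant effect is partly a chosen target.** Section 6 says it reports effects of participation, and leaving out people who never had the year-2 check fits that aim. The exclusion is then not an error in itself. What remains is that the population-level objective has no direct analysis for these outcomes.
- **The plan is aware of the problem.** It warns that exclusion is likely to cause selection bias, and it plans sensitivity analyses for missing data, balance checks and the register benchmark. The benchmark can reveal residual bias in register outcomes but corrects nothing in the measured ones. No consequence is stated if a check fails.
- **The bias sizes depend on modelling choices.** One health variable drives attendance and is also the outcome, and weighting CG by p is an inference. SCORE contains age and gender (section 3.1) and may be more stable than 0.8. At correlation 0.95 under B, unweighted bias reaches +0.17 SD and the weighting removes most of it.

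A reader might infer that section 6 restores none of the dropped IG members. The text does not support that: the imputation group can include year-2 attenders who did not return (also up to 1,300 at r = 0.55). Only the year-2 skippers are clearly left out. A reader might also take -0.2 SD as the bias in this trial. The SAP gives neither the return rate nor the reasons for returning, so no such figure follows; -0.21 is a corner of the grid at correlation 0.5.

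**Conclusion.** The point holds for CVD risk, fitness, activity and self-rated health. The two-versus-one rule is explicit, the year-2 skippers with measured outcomes are not brought back, and for CVD risk and activity the CG score contains CG's own outcome. The sets compared are not those that randomisation balances.

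Whether the weighting repairs this depends on why people return and how stable the outcome is. The remaining bias is about 0 if return follows current health. If return follows year-2 results it is up to about -0.2 SD at correlation 0.5 and about 0.02 SD or less in size at 0.95, against an SE near 0.03. These are illustrations under assumed attendance models. They show that the repair is not assured, not that it fails here. The matter should be fixed, but the planned analysis need not be abandoned.

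**What to change.** 1. **Add an analysis for the population-level objective.** Compare all year-5 attenders (or responders) in IG with all those in CG, whatever the IG members did in year 2. Weight each arm to all randomised, using register covariates taken at one common pre-invitation date. Report year-5 attendance by arm.
2. **Keep the propensity-weighted analysis, labelled as a participant-effect analysis.** State the weight formula and which arm is weighted. Add a sensitivity analysis whose score uses only covariates measured before the first invitation in both arms. This should not be presented as removing the bias: in the models above, a register-only score leaves it near the unweighted level (A -0.03 to +0.14, B -0.09 to +0.10, C -0.15 to -0.02).
3. **State which analysis is main**, and that the participant analysis is reported as associational if the balance or register check fails.

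The cost is SAP wording and no new outcome data, provided suitable register covariates are available at a common date. Analysis 1 estimates the effect of the offer. An effect confined to year-2 attenders is diluted to their share of IG year-5 attenders (0.55 to 0.91 in the grid). It is also not always less biased. If the year-2 check itself changes who attends in year 5, bias remains: about -0.05 to -0.12 SD where return is unrelated to health, which exceeds that of CG weighted by p in 97% of those settings. Where return follows year-2 results, its bias is smaller than that of CG weighted by p in every setting. That is why it is added alongside the planned analysis and does not replace it.

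### Section 4 restricts the register-based functional-capacity outcomes to attenders, section 6 benchmarks them against everyone invited, and the SAP never says which is the main result

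*SAP*

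**What the plan says.** Section 3.4 says functional capacity (work participation and sick leave) "will be assessed based on the national register of social transfer payments (DREAM"), a national register. Attendance plays no part in observing it.

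Section 4 announces that "The actual study population will differ according to the different outcome measures", and then gives for this outcome: "Functional capacity: The study population is all individuals from IG, who participated in both baseline and re-examination", together with all CG members who attended their examination. This is the same rule as for CVD risk and fitness, which cannot be measured without attendance. IG is the group "invited to attend the health check in year 2 and re-invited in year 5"; CG is invited in year 5 only.

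Section 6 takes a different line. It introduces its imputation and weighting strategy with "For the outcomes, which are only measured for participants in the re-examination (CVD risk, physical activity and self-rated health"), and functional capacity is not on that list. Under the propensity-score heading, the attender strategy is imitated for functional capacity and compared with estimates in everyone invited, to see whether the score removes bias. The missing-data text adds: "The mimicked analysis based on outcomes available from register-data also allows assessment of the potential violation of the MAR assumption". The closing reporting sentence speaks, for every outcome, of effects tied to taking part in the programme. No sentence calls either functional-capacity estimate the main one.

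**The concern.** For examination and questionnaire outcomes, restriction to attenders is hard to avoid, and section 6 adds methods to deal with it. For register outcomes it is a choice. The section 4 set is formed after randomisation and by a different rule in each arm: two attendances in IG, one in CG. People who return for a second check may differ in employment and sick leave from those who do not, and CG has no matching second filter. The comparison then loses the protection of randomisation although the outcome could be available for everyone.

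Section 6 obliges the analyst to compute both estimates. The risk is therefore which one is presented as the trial's result, possibly after both have been seen. Section 1 states the objective as effectiveness at population level, and the attender estimate does not answer that. Section 6's own warning about selection bias concerns missing outcome data; it applies here by analogy only.

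**Working it through.** **Plan's own figure.** Two of five randomised groups: 2/5 × 26,216 = 10,486, against 10,505 stated in section 4. The difference is 0.2%, so they agree. The SAP gives no power calculation to reproduce.

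**The passages side by side.**

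| Place | Population for functional capacity | Status given |
|---|---|---|
| Section 4 | IG attending twice, CG attending once | the study population, unqualified |
| Section 6, opening | not among the attender-only outcomes | – |
| Section 6, propensity score | attenders | imitation, to test the method |
| Section 6, propensity score | everyone invited | reference for judging bias |
| Section 6, reporting | not named; effects of taking part | reported for each outcome |

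Section 4's study population is thus the set whose bias section 6 intends to test.

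**How many section 4 keeps.** From the SAP: 10,505 people and 55% attendance ("We expect a similar proportion of the population will participate in the following years"). Assumed: equal arms (5,252.5 each) and a return rate r among IG first attenders. CG = 0.55 × 5,252.5 = 2,889; IG = 2,889 × r.

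| r | IG | CG | Total | Share of 10,505 |
|---|---|---|---|---|
| 0.55 | 1,589 | 2,889 | 4,478 | 43% |
| 0.85 | 2,456 | 2,889 | 5,344 | 51% |
| 1.00 | 2,889 | 2,889 | 5,778 | 55% |

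**What selection could do (illustration, unweighted comparison, no true effect).** Let q = 1 − r, d = returner minus non-returner difference in work fraction, and e = IG first attenders minus CG attenders. The mean of IG first attenders lies q × d below that of returners, so

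bias = q × d + e.

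Two-sided error = Φ(−1.96 + k) + Φ(−1.96 − k) with k = bias/SE; it reaches 10% at k = 0.652. SE = 0.35 × √[DE × (1/IG + 1/CG)], with SD 0.35 and design effect DE assumed. The last column takes e = 0.

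| r | DE | SE | Bias giving 10% error (0.652 × SE) | d needed (bias/q) |
|---|---|---|---|---|
| 0.85 | 1 | 0.0096 | 0.0063 | 0.042 |
| 0.85 | 1.5 | 0.0118 | 0.0077 | 0.051 |
| 0.55 | 1 | 0.0109 | 0.0071 | 0.016 |
| 0.55 | 1.5 | 0.0134 | 0.0087 | 0.019 |

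Multiplied by 52 weeks, the tipping bias is 0.33–0.45 weeks a year.

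The groups first attend in year 2 and year 5, so e = 0 is itself an assumption. At r = 0.85 and d = 0.05, bias = 0.0075 + e:

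- e = −0.02 gives −0.0125 (error 26% at DE 1, 19% at DE 1.5);
- e = −0.01 gives −0.0025 (about 6%);
- e = +0.02 gives +0.0275 (82% and 65%).

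With d = 0 and e = 0 the error stays at 5%.

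For sick leave as yes/no, with prevalence p of 5–15% assumed, SE = √[DE × p(1 − p) × (1/IG + 1/CG)]. The tipping bias runs from 0.39 percentage points (p 5%, r 0.85, DE 1) to 0.89 (p 15%, r 0.55, DE 1.5).

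**The case against.** The strongest reply is that the randomised comparison is not lost. Section 6 plans the all-invited estimate, treats it as the standard and accounts for household clustering throughout. That stands, and it makes this a problem of labelling and hierarchy rather than of a missing analysis. It does not remove the unqualified sentence in section 4.

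Second, the error figures describe an unweighted attender comparison, whereas section 6 would weight, and weighting is aimed at the q × d term. This is partly right. However, section 6 introduces imputation and weighting as additional, which implies a base analysis in the section 4 sets. Weighting also relies on a comparability of first attenders across arms much like e = 0. The inputs are assumed, so the figures show that selection could matter, not that it does.

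Third, the reporting sentence may show that the participation effect was the intended target throughout. If so, the SAP should say so and explain why the main result is the one it proposes to validate against another.

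Fourth, the attender analysis can have more signal. This is true, and it is counted as a cost under the fix.

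**Conclusion.** The concern holds. Section 4 fixes as study population, for register outcomes, a set selected after randomisation and differently by arm. Section 6 contradicts its status by using everyone invited as the reference, and the SAP does not say which result leads. This should be corrected, although the randomised estimate will be computed in any case.

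The textual conflict rests on no assumption. The share kept (43–55%) uses the SAP's 55% and 10,505 with assumed equal arms and return rate. The tipping bias (0.0063–0.0087 of full time) further assumes the SD and design effect. The documents give none of q, d or e, so the actual bias may be larger, smaller, reversed or nil.

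**What to change.** 1. Section 4, replace the functional-capacity sentence with:

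> Functional capacity: the main analysis includes all individuals randomised to IG or CG with register data, regardless of attendance, analysed as randomised and accounting for household clustering. Numbers without register data are reported by group. The analysis of attenders is secondary and serves to check the propensity score (section 6).

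2. Section 6, replace the reporting sentence with:

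> For functional capacity the main reported effect is that of being invited (all randomised, IG versus CG). Effects of taking part are reported for the examination and questionnaire outcomes and, as secondary results, for functional capacity. All effects are given with 95% confidence intervals.

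3. A minor clarification in section 3.4, where the text reads "Work participation will be described as a fraction of full-time employment in the 52 weeks before the invitation date" although IG has two such dates. Section 1's description of impact after follow-up leaves year 5 as the only workable reading; say so for both work participation and sick leave: the year-5 invitation in CG, the year-5 re-invitation in IG.

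**Cost.** Wording only, since the all-invited estimates are already planned. The real price is dilution. If people who never attend gain nothing and IG non-returners gain as much as returners, the effect of the offer is 0.55 of the effect of attending (1/0.55 = 1.82). The attender SE is √[(1/IG + 1/CG)/(2/5,252.5)] = 1.41 times (r 0.85) to 1.60 times (r 0.55) the all-invited SE, with the same design effect assumed. Bias apart, the attender analysis then has 1.82/1.41 = 1.29 to 1.82/1.60 = 1.14 times the signal-to-noise ratio. If non-returners also gain nothing, the factors are 1/(0.55 × 0.85) = 2.14 and 1/(0.55 × 0.55) = 3.31, and the advantage is 2.14/1.41 = 1.52 to 3.31/1.60 = 2.07. The change claims no gain in precision. Its case is avoidable selection and the population-level objective.

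### The section 6 return model counts IG death or loss of eligibility before year 5 as declining, and is then applied to CG attenders who were all alive and invited in year 5

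*SAP*

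**What the plan says.** Section 4 (Analysis Population) sets the two arms on different clocks. "The Intervention group (IG) was defined as the population invited to attend the health check in year 2 and re-invited in year 5". CG has a single invitation, in year 5. An IG member can therefore enter in year 2; a CG member can enter only in year 5.

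Section 6 adds a second strategy for CVD risk, physical activity and self-rated health. Its first step is imputation: "we will use multiple imputation to impute missing values for all who participated in the health checks when randomized to receive it", in both arms (the comparison arm is printed there as RG). Under Missing data, missingness is to be reported "with information on reasons (did not receive health check, did not answer question"; death and departure are not listed. The same part says: "Multiple imputation will be performed for missing outcomes as described in section 4 by inclusion of baseline characteristics that can explain the missingness". One missing-at-random assumption covers everything.

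Under Propensity score the plan states: "Among all individuals in IG who participated in year 2 examination, we predict the likelihood of participation in the re-examination in year 5". The fitted model then supplies a propensity for every initial-check attender in either arm, which means year-2 attenders in IG and year-5 attenders in CG. The outcome analysis is weighted by that score.

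**The concern.** Between year 2 and year 5 an IG attender can fail to be re-examined for two kinds of reason: the person has died or is no longer eligible for re-invitation, or the person is alive and invited but does not come. Section 6 codes both as non-return. For CG attenders the first kind cannot occur, because being examined in year 5 shows that they were alive and invited.

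A score that mixes the two therefore means something different in each arm. Its stated purpose is to make the arms comparable. Used as a weight in CG, it moves CG towards covariate patterns that predict staying, although CG has already been filtered on staying. Age is one such covariate and is also an input to Heart-SCORE, so the CVD-risk comparison is exposed.

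A second problem arises only if year-5 outcomes are imputed for IG members who did not return. Nothing then excludes those who died, and a missing-at-random model for self-rated health or activity after death has no meaning.

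**Working it through.** **Inputs from the SAP.** 26,216 randomised into five groups; 10,505 in the trial; 55% attendance in year 1, with a similar share expected later (all section 4). The SAP gives no rate of death, departure or re-attendance, no effect size and no weight formula. Every rate below other than the 55% is an assumption.

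**Step 1: who is in IG and CG.** Two of five groups would be 26,216 × 2/5 = 10,486, against the stated 10,505 (0.2% apart). The trial count thus matches two whole randomised groups, not groups already reduced to those present in year 5.

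**Step 2: what the return model estimates.** For covariates x, let f(x) be the randomised population, A(x) the chance of attending the first check, S(x) the chance of being alive and still eligible for invitation in year 5, and R(x) the chance of returning if invited. Assume that f, A and S are the same functions in both arms.

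- IG re-attenders: f · A · S · R
- CG attenders, unweighted: f · A · S
- Score fitted among all IG year-2 attenders: S · R
- CG weighted by that score: f · A · S² · R
- Score fitted only among those alive and eligible in year 5: R
- CG weighted by the restricted score: f · A · S · R, which matches IG re-attenders

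The surplus factor S(x) is the defect. It matters only so far as S varies with x. The algebra assumes that CG is weighted directly by the score, which the SAP does not specify.

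**Step 3: size through the weights.** Assume that CG attenders are uniform in age, and that 15% of the younger half and 5% of the older half leave. The surplus weights are 0.85 and 0.95.

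- Weight on the older half: 0.95 / (0.85 + 0.95) = 0.528, a shift of 0.028 from 0.5
- Distance between the two half-means, uniform distribution: 1.73 SD
- Shift in CG mean age: 0.028 × 1.73 = 0.048 SD of age

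For an outcome linear in age, the CG mean shifts by 0.048 SD times its correlation with age: 0.024 SD at an assumed correlation of 0.5, and 0.048 SD as the ceiling.

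**Step 4: size through imputation, if non-returners are imputed and enter the comparison.** If a share p of IG has no CG counterpart and differs by d SD, the unweighted IG mean shifts by p × d.

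- Deaths only, p = 0.4%, d = 0.5: 0.004 × 0.5 = 0.002 SD
- Deaths and departures, p = 5%, d = 0.2: 0.05 × 0.2 = 0.010 SD
- Deaths and departures, p = 15%, d = 0.3: 0.15 × 0.3 = 0.045 SD

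**Step 5: the yardstick.** With equal arms, attenders per arm are 10,505 / 2 × 0.55 = 2,889. The SE of a mean difference is √(2/2,889) = 0.026 SD, and the 95% half-width is 1.96 × 0.026 = 0.052 SD. This ignores clustering, weighting, imputation and the smaller number of IG re-attenders, so the real interval is likely to be wider.

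**The case against.** A reader might infer that the SAP imputes year-5 outcomes for everyone in IG who died or moved, while their CG counterparts drop out. The documents do not support that as a statement of fact.

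- The SAP nowhere says that such people are imputed. It speaks of missing values and ties outcome imputation to section 4, where the IG set is those assessed on both occasions. Weighting by the propensity to return also fits a comparison of re-attenders better than one in which every year-2 attender has an imputed outcome. Against this, not having received the check is a listed reason for a missing outcome, and among re-attenders nobody would fall under it. The text is ambiguous, and the imputation harm is conditional.
- Death and moving differ. A mover has a real blood pressure and activity level in year 5, and imputing these is ordinary handling of loss to follow-up. The SAP does not say whether people who leave the municipality stop being invited, so the absence of CG counterparts is certain for deaths only.
- IG is defined as re-invited in year 5, which could be read as excluding people who died or left. The count in step 1 suggests otherwise, and the return-model sentence covers all IG year-2 attenders. Figure 1 or the protocol may settle who is re-invited, but section 6 refers to no such rule.
- The plan has checks: sensitivity analyses for departures from missing at random, and a repeat of the strategy on register outcomes compared with the whole invited population. These might signal residual bias. They cannot attribute it to death or departure, or correct CVD risk, activity or self-rated health.

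None of this removes the return-model point, which holds whether or not non-returners are imputed.

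**Conclusion.** The point holds for the return model. Followed as written, it mixes being present in year 5 with choosing to attend, and it is carried to a group already conditioned on presence. Imputation after death is a risk only on one of two open readings.

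The size is modest. Deaths alone are negligible for means at this age, at about 0.002 SD under the assumed rates. Anything material depends on how many leave, how strongly leaving relates to the outcome's predictors, and whether leavers are still invited. With an assumed 5–15% leaving, both routes give at most a few hundredths of an SD, below the ideal half-width of about 0.05 SD but not trivially small beside it at the upper end. The direction is not established: in the age illustration CG becomes older, but only because younger people were assumed to leave more often.

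The section 4 comparison of examined participants is not affected, since both arms there were assessed in year 5. The correction is worth making because it removes a known mismatch at very little cost.

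**What to change.** In section 6:

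1. Fit the return model only among IG year-2 attenders who were alive and eligible for re-invitation at the year-5 invitation date, the condition that CG attenders already meet.
2. Apply the same restriction to any imputation of year-5 outcomes, and state that no outcome is imputed after death.
3. State whether IG non-re-attenders enter the weighted comparison, and give the form of the weight.
4. State whether people who leave the municipality are still invited. Add death and having left or not been re-invited to the reasons for missingness, as separate categories tabulated by arm.

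The cost is a few sentences and one eligibility flag. The IG modelling set becomes slightly smaller, and the result applies to people still present in year 5.
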